GIRLS INVEST

Methods Protocol

CLINICAL TRIALS UNIQUE ID: NCT06942481

April 23, 2025

METHODS

This study involved a two-arm cluster randomized controlled trial among 258 adolescent females ages 15-19 years in 16 secondary schools within low-income communities from two Local Government Areas (LGAs) with the highest concentration of low-income communities within Ibadan, Nigeria. Low-income communities were of particular focus considering the intersection of economic vulnerability and IPV risk^{1,2}. Sixteen schools within low-income communities were selected from the 28 schools approved by the Ministry of Education; schools were randomized to treatment assignment (Girls Invest intervention or wait-list control group) using a randomizer software package after baseline data collection. The wait-list control groups were provided with referrals to local support organizations, as the standard of care, and received Girls Invest subsequent to the six-month follow-up data collection. The study protocol was approved by the Human Research Protection Program at San Diego State University (HS-2021-0031) in the US and the University of Ibadan / University College Hospital Joint Institutional Review Board, in Nigeria (UI/EC/21/0183). Letter of approval was obtained from the Oyo state Ministry of Education, Nigeria and permission obtained from the Principals of each school.

Intervention Description

The Girls Invest intervention involved: 1) app-based trainings on topics related to financial literacy, gender equity, and health and 2) financial resources/incentives supporting girls' education/career.

Girls Invest trainings promote financial literacy and aim to raise girls' critical consciousness related to gender-based economic and social constraints that promote IPV (e.g., economic constraints that promote financial dependence on male partners, social norms that support IPV). Girls Invest app trainings encouraged girls to reflect on traditional gender norms that disfavor girls' future trajectories. Trainings supported gender equitable beliefs and attitudes that promote girls' educational/economic endeavors, health and well-being, and power or control within their families and relationships. In order to complete each module and advance to the next level, girls needed to perform satisfactorily on topic quizzes. App content was interactive and included real life scenarios to maximize girls' engagement. Additionally, to further support engagement and maintain girls' interest and attention, each training was designed to take approximately 20-25 minutes for girls to complete. Participants were provided access to a smartphone to complete the app training modules. The smartphones were kept with the research team and girls could use them after school. To reinforce learning, a booklet containing the content of the app training was given to each girl after completion of the mobile app learning. App training module topics included:

1. **Gender roles and goal setting** covers what gender roles are and how they affect girls' education, career, body image, power in family and relationship decision-making, property rights, and rights over their bodies, including harmful traditional practices. Trainings emphasize the ways in which gender-based discrimination influences girls' health, development, and future trajectories.
2. **Sexual and reproductive health and rights** promotes investing in a "healthy future," covering information on menstruation, sexual health, abstinence, sexual consent, negotiating condom use, sexual risk behaviors for unintended pregnancy and sexually transmitted infections, information on family planning methods, girls' sexual and reproductive decision-making power, and reproductive coercion (e.g. male partners' coercing girls to get pregnant or sabotaging girls' intentions to use family planning).
3. **Money, power, and relationships** discusses the subtle ways in which economic reliance on male partners can decrease girls' decision-making in relationships and increase risk for IPV. This module covers healthy and unhealthy relationships, including warning signs for IPV. Topics on IPV also include how to identify it, resources to get help, how to support peers experiencing IPV, and the effects across all aspects of girls' lives. This module uses story-based curricula to improve awareness and early detection of IPV. It also covers the consequences of IPV, such as effects on mental health

and substance use.

4. **Financial literacy basics** contains information on money management, savings, thrift, accounting, interest, budgeting, loans, investing, financial security and independence. This knowledge is key to supporting young women to be economically self-sufficient thereby, reducing girls' vulnerability to IPV, including leaving abusive relationships.⁴³
5. **Future aspirations** covers preparation for apprenticeships, getting a job, going for higher education, deciding on a future career, and other relevant topic areas to support girls' future financial and entrepreneurial goals. This module provides vignettes from diverse women doing different types of jobs/businesses.

[figure not shown]
Financial resources provided to girls included paying for examination fees schools required for girls to continue / further their education or purchasing an item to support apprenticeship such as a sewing machine, baking oven and pans, or hair dryers (equivalent to N65,000, approximately 100USD). These financial resources were identified by girls participating in the intervention and were chosen over cash transfers to better ensure that participants had ownership of the resource/incentive (i.e., rather than cash transfers that could be used by the family and not fully directed at the needs of girls).

Recruitment

The school authorities were visited by research team to inform them about the study process. Each school provided a focal person (class teacher), who worked with the research team to coordinate recruitment. Trained research staff, with the assistance of the focal person visited each class to explain the study and the Girls Invest intervention. Girls in senior secondary classes one and two (years 10 and 11) in each of the 16 schools and who were between the ages of 15-19 years were offered to participate in the study. Those interested in participating signed the consent form; those who were under 18 years old had parents sign a consent form as well. Parents were invited to the schools and informed about the study process.

Sampling of the participants, including the numbers approached, as well as those eligible (those ages 15-19) and interested is illustrated in Figure 1. Those approached but not eligible were due to them being under age 15.

Figure 1. Consort Diagram

*Number of individuals assessed for eligibility, number excluded and number that declined to participate are estimated based on the number of students per class in each school.

Data Collection Procedures

Data collected for this study were drawn from process evaluation program monitoring data, participant surveys, and focus group discussions. All participant data were collected between September 2023 and July 2024.

Process evaluation monitoring data were used to report completion rates of the app-based trainings. Data were collected via the app to describe whether participants completed all trainings, and for those with partial completion, how many of the five trainings participants completed. Program monitoring data included app generated data on how long participants spent on each training. Program monitoring data also documented the provision of the economic incentives based on app-training completion.

Surveys were conducted with all participants at baseline and at a six-month follow-up timepoint. The survey collected data on girls' experiences of IPV, gender-based attitudes, and perceptions of economic vulnerability as well as demographic characteristics. Research staff administered the survey in a one-on-one private setting. The survey took about 45 minutes to complete; participants received N4,000 for the baseline survey and N6,000 for the follow-up survey as compensation for their time. The follow up rate was 69% among intervention and control groups, with no significant difference in follow-up by treatment group ($p=0.72$).

Focus group participants ($n=62$; approximately 12-13 participants in each of 5 focus groups) were drawn from study participants who had completed the Girls Invest intervention. Participation was voluntary and demographics matched those of the larger sample. After completing the six-month follow-up survey, participants who voiced interest in participating in the focus groups were contacted to schedule the focus group. Trained and experienced facilitators conducted informed consent among all focus group

participants and subsequently conducted the focus group, which lasted about 60-90 minutes and took place in a private room. Participant satisfaction and acceptance of the intervention were assessed, as well as how app-based trainings impacted participants' knowledge, attitudes, and beliefs regarding Girls Invest topics. Participants were reimbursed N6,000 upon completion of the focus group discussions. Focus group discussions were digitally recorded, transcribed, and de-identified.

Measures

Program monitoring data were automatically downloaded from the app, generating a spreadsheet providing information on module completion, including the time spent on each module. Additional process data were recorded by research staff regarding the provision of the financial incentives upon app-based training completion, including the type of financial incentive received.

Survey measures included sample characteristics as well as gender attitudes and economic factors associated with IPV.

Sample Characteristics: Survey measures included the following sample characteristics: age, ethnicity (Yoruba, Ibo, Hausa, Other), religion (Christianity, Islam, Other), relationship status (currently in a relationship, have ever has a relationship but not currently, never had a relationship), employment (yes/no), apprenticeship training (yes/no), and living situation (living with parents, other family, or others).

Attitudes supportive of traditional gender roles were measured by seven items assessing male and female roles in the following: decision-making (e.g., when to have sex, household purchases), household chores, childcare, reproductive decisions (including pregnancy prevention), and in receiving education/training. Responses involved 5-point Likert scales ranging from strongly agree to strongly disagree. Summary scores were calculated for the three items, with a Cronbach alpha of 0.60, indicating adequate internal consistency.

Attitudes supportive of IPV were measured using 7 validated items adapted from Demographic Health Surveys asking whether any of the following scenarios a husband has good reason to hit his wife: (1) She does not complete housework to his satisfaction, (2) She disobeys him, (3) She refuses to have sexual relations with him, (4) She asks him whether he has other girlfriends, (5) He finds out she has been unfaithful, (6) She goes out without telling him, or (7) She does not prepare a meal to his satisfaction. Responses involved 5-point Likert scales ranging from strongly agree to strongly disagree. Summary scores were calculated for the three items, with a Cronbach alpha of 0.89, indicating high internal consistency.

Coping with experiences of gender-based discrimination included three items assessing perceived ability to identify instances of "gender-based discrimination against me" and coping with such experiences as being able to "take care of myself," and recognizing that such experiences are not "about anything I did as an individual". Responses involved 5-point Likert scales ranging from strongly agree to strongly disagree. Summary scores were calculated for the three items, with a Cronbach alpha of 0.65, indicating adequate internal consistency.

Perceptions of economic vulnerability were assessed using eight items asking about perceived household economic situation, including having enough money to purchase basic necessities (e.g., food, clothes, other needs) and money to pay for education/training of the participant. Items also assessed perceived financial stress of the household. Responses involved 5-point Likert scales ranging from strongly agree to strongly disagree. Summary scores were calculated for the three items, with a Cronbach alpha of 0.60, indicating fair internal consistency.

Focus group guides were developed to 1) provide feedback on the intervention, including the app-based platform and financial incentives provided and 2) to understand the impact of participating in Girls Invest. Specifically, participants were asked to describe their opinions about the use of an app as a model of intervention delivery, as well as their satisfaction with the app training curriculum and financial incentives. The focus groups also addressed how each training topic had impacted the participants' knowledge, attitudes, and beliefs regarding economic and gender related factors that promote IPV (e.g., economic vulnerability, gender norms that support IPV).

Data Analysis

Quantitative survey data were used to describe the sample characteristics, and combined with program monitoring data to assess the proportion of participants completing the app-based trainings, how long participants spent on each training, and whether they received financial incentives based on app training completion, as well as what type of financial incentive they received.

A difference-in-differences approach was used to assess changes between baseline and follow-up in: 1) attitudes supportive of traditional gender roles, 2) attitudes supportive of IPV, 3) coping with experiences of gender-based discrimination, and 4) perceptions of economic vulnerability. The primary analysis was conducted using a linear regression model with cluster-adjusted standard errors to account for intra-cluster correlation. The model included an interaction term between time (pre/post) and study arm (intervention/control) to estimate changes over time associated with the intervention. Given that there were no statistically significant differences in demographic factors at baseline between the intervention and control groups (indicating effective randomization of treatment group assignment), we did not include covariates in the models. Analyses used an intention-to-treat (ITT) approach, with sensitivity analyses conducted to assess robustness to missing data and alternative model specifications. All analyses were performed using SAS v9.4.

For analyzing the focus group data, an inductive, content analysis approach was used. Content analysis involves generating and applying codes to sections of text, then reviewing the text by various codes and 'code families' to identify recurring themes. The coding team created an initial list of codes based on key domains and used these to code discussions. To enhance coding agreement, data were individually coded by two researchers, and coding procedures and definitions were discussed and compared for agreement. Additions of new codes or changes in code definitions were determined via consensus among the research team. Additional codes related to participants sharing information they learned in the app trainings were created to reflect these emerging themes. No new codes emerged after two-thirds of the focus groups were coded, suggesting that content saturation was achieved. For this particular analysis, we retrieved coded text on themes related to acceptability with the program as well as economic and social impacts. Inter-coder reliability was assessed, with 80% coder consistency or higher between coders deemed sufficient for inter-coder reliability.

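### The economic-vulnerability score covers money for the girl's education or training, which the programme pays for in one arm, so the total alone cannot show a wider change

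*Combined protocol and SAP*

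**What the plan says.** Measures describes the outcome: "Perceptions of economic vulnerability were assessed using eight items asking about perceived household economic situation". The content covers basic necessities, household financial stress and "money to pay for education/training of the participant". On scoring it says: "Summary scores were calculated for the three items, with a Cronbach alpha of 0.60, indicating fair internal consistency". Eight items are described but three are said to be scored. The same phrase follows both seven-item scales, so it may be carried-over wording, but the text does not settle it.

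Intervention Description gives the financial component: "Financial resources provided to girls included paying for examination fees schools required for girls to continue / further their education". The alternative to a fee payment was equipment for learning a trade, and the section puts the value at N65,000 (about 100 USD). Under Data Collection Procedures, monitoring data "documented the provision of the economic incentives based on app-training completion". The opening paragraph of Methods says that wait-list girls got referrals, and Girls Invest itself only after the six-month data collection.

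Data Analysis lists "4) perceptions of economic vulnerability" as the last of four difference-in-differences outcomes. The sensitivity analyses named there concern missing data and model specification. None concerns item content.

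**The concern.** Before follow-up, the intervention arm alone is offered something that part of the outcome asks about. If a girl's examination fee is paid, or her training equipment is bought, she may answer the education/training content more favourably while her view of food, clothing and household financial strain stays the same. The total would still fall.

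Measures presents this outcome among the economic factors associated with IPV. A lower total would naturally be read as girls feeling less economically vulnerable in general. The total cannot distinguish that from relief of the one need the programme paid for. Data on receipt and type of resource were recorded, but Data Analysis uses them only descriptively.

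**Working it through.** The documents give no power calculation, SD or effect size for this outcome, so there is no figure to reproduce. The arithmetic below shows scale only.

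**From the documents:** eight items, alpha 0.60, five response options, 258 girls, 16 schools, 69% followed up.

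**Assumed:** equal item variances; item SD 1.2 (range 1.0 to 1.4); one, two or three overlapping items (the number is not stated); a full one-point shift in the arm mean on those items and none elsewhere; eight schools per arm; ICC 0.01 to 0.10; change-score SD equal to score SD, that is, a baseline to follow-up correlation of 0.5.

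**Step 1, spread of the total.** Mean inter-item correlation = alpha/(k − alpha(k − 1)) = 0.60/(8 − 4.2) = 0.158. SD of the sum = 1.2 × √(8 × (1 + 7 × 0.158)) = 1.2 × 4.10 = 4.92 (4.1 to 5.7 over the item-SD range).

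**Step 2, shift from the overlapping items alone.**

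| Overlapping items | Shift, item SD 1.2 | Range, item SD 1.4 to 1.0 |
|---|---|---|
| 1 | 1/4.92 = 0.20 SD | 0.17 to 0.24 |
| 2 | 2/4.92 = 0.41 SD | 0.35 to 0.49 |
| 3 | 3/4.92 = 0.61 SD | 0.52 to 0.73 |

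**Step 3, what the trial can distinguish from zero.** Followed: 258 × 0.69 ≈ 178, or 89 per arm and 178/16 = 11.1 per school. SE = √(2 × DEFF/89), with DEFF = 1 + 10.1 × ICC.

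- ICC 0.01: DEFF 1.10, SE 0.157.
- ICC 0.10: DEFF 2.01, SE 0.213.
- Significance threshold, 2.145 × SE (t, 14 df): 0.34 to 0.46 SD.
- Detectable with 80% power, (2.145 + 0.868) × SE: 0.47 to 0.64 SD.

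**Step 4, comparison.** One item stays below the threshold throughout. Two items, at 0.41, exceed it only for an ICC below about 0.06: (0.41/2.145)² × 89/2 ≈ 1.6 = DEFF. Three items exceed it throughout.

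**Step 5, sensitivity.**

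- *Correlation.* The SE scales by √(2(1 − ρ)). With ρ = 0.3 the threshold is 0.40 to 0.54; with ρ = 0.7 it is 0.26 to 0.35. One item still falls short in both cases and three still exceed it. Two are borderline at 0.3 and exceed it at 0.7.
- *Receipt.* If the one-point shift occurs only in girls who received a resource, each shift is multiplied by the proportion who did. The two-item shift then misses even the lowest central threshold once receipt is below 0.34/0.41 ≈ 83%.
- *Three items scored.* Correlation = 0.60/(3 − 1.2) = 0.333; SD of the sum = 1.2 × √5 = 2.68. One overlapping item is a third of the score and moves it by 1/2.68 = 0.37 SD, inside the threshold range. The documents do not show whether the education/training item is among the three.

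**The case against.** The strongest reply is that this is an intended effect. Financial resources are one of the two stated components, and being unable to afford one's schooling is part of economic vulnerability. The randomized comparison captures that relief correctly. This stands: a reader might infer that the intention-to-treat estimate is biased, and the documents do not support that. The limitation is on what the total can be said to mean.

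Second, the items ask about the household's situation and the resource was not cash, so a girl could still report that her household lacks education money. Item wording is not given, so the size and even the direction are unknown. This also stands: receipt of the programme cannot be equated with a changed answer. Nor is delivery before the survey stated. It is only made likely by resources following training completion and by focus groups, held after the survey, asking completers about the incentives.

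Third, the text names one topic, which may be one item. A reader might go further and infer that the overlap could account for the whole of any observed effect. The documents do not support that: they report no result for this outcome, and with eight items scored a single overlapping item falls short of significance even under a generous shift (one point is 1/1.2 = 0.83 of an assumed item SD).

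Fourth, data collection ended in July 2024, so an added analysis would be post hoc, and a shortened score invites reading an inconclusive result as no wider effect. Both are fair, and both can be met by labelling and by reporting intervals. What the reply leaves untouched is that nothing planned shows whether a difference extends past the need that was paid for.

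**Conclusion.** The point holds as a limit on interpretation. The overlap between outcome content and programme payment is in the text, it arises in one arm only, and no described analysis addresses it. Its size cannot be known from the documents. Under the stated assumptions one overlapping item would not produce significance by itself, two would only at low ICC, and three would across the ICC range; incomplete receipt reduces all of these. These figures rest on the assumed item SD, number of items, one-point shift, allocation, ICC and correlation. The interpretive limit rests on none of them. It rests only on the described content and on resources having reached girls before the six-month survey, which is probable but not stated.

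**What to change.** Keep the existing summary score as the outcome. In Data Analysis, add a supplementary analysis using the same difference-in-differences model and standard errors with the education/training item(s) left out. Choose the items by content, not by results, and label the analysis post hoc if it is done after data collection. Report the omitted item(s) separately with confidence intervals. In Measures, state whether eight or three items are scored, which they are, and how many concern education or training. In Intervention Description or Data Collection Procedures, state when resources were delivered relative to the six-month survey.

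Limit any claim about wider economic vulnerability to what the reduced score supports, and do not read a non-significant reduced score as proof of no wider effect.

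The cost is small: further model runs on data already collected, plus a few sentences. The price is reliability. By Spearman-Brown, alpha = k × 0.158/(1 + (k − 1) × 0.158), which is about 0.57 with seven items, 0.53 with six and 0.48 with five, so the interval on the reduced score will be wider in SD terms.

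### With only 16 randomized schools, the four intervention-effect tests use cluster-adjusted standard errors and no stated small-sample method; read in the ordinary way, this runs above the nominal 5%

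*Combined protocol and SAP*

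**What the plan says.** The opening paragraph of Methods describes a "two-arm cluster randomized controlled trial among 258 adolescent females ages 15-19 years in 16 secondary schools". It makes the school the unit of allocation: "schools were randomized to treatment assignment (Girls Invest intervention or wait-list control group". Under Data Collection Procedures, each girl is surveyed at baseline and at six months, and "The follow up rate was 69% among intervention and control groups".

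Data Analysis lists four outcomes: attitudes to gender roles, attitudes to IPV, coping with discrimination, and perceived economic vulnerability. It then states the method: "The primary analysis was conducted using a linear regression model with cluster-adjusted standard errors to account for intra-cluster correlation". The effect is the interaction of time and arm, without covariates. The section adds "Analyses used an intention-to-treat (ITT) approach", with "sensitivity analyses conducted to assess robustness to missing data and alternative model specifications", and "All analyses were performed using SAS v9.4".

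The document names no variance estimator, finite-cluster correction, reference distribution, degrees of freedom or SAS procedure. It also gives no significance level, ICC, power calculation or distribution of school sizes.

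**The concern.** Because schools were allocated, the comparison of change between arms rests on 16 independent units, however many girls are surveyed. A sandwich variance is justified by a large number of clusters. With about 8 per arm, the uncorrected form underestimates the variance, and a normal reference ignores the uncertainty of an estimate built from so few schools. Both errors narrow the intervals and lower the p-values.

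Every intervention-effect p-value and interval comes from this one model. A result near the 5% boundary cannot be interpreted without knowing which form of adjustment produced it.

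**Working it through.** The document gives no error rate or sample-size figure to reproduce, so the check asks what the stated method delivers with 16 schools.

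**Inputs from the document:** 16 schools, 258 girls (258/16 = 16.1 per school), 69% followed up (0.69 × 258 = 178), two surveys, linear model with time, arm and their interaction.

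**Assumed, not in the document:** two-sided 5% level; 8 schools per arm (the CONSORT figure is not reproduced in the text available, so this is not held against the plan); for the simulations, also ICC, the share of school variance stable over time, within-girl correlation and the CV of school size.

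**Closed form, equal schools, 8 versus 8.** The interaction estimate is then the difference between arms in mean school-level change. With an ordinary two-sample standard error across schools, its ratio T follows t on 14 df under no effect (normal school-level changes, equal variance). The uncorrected sandwich divides by 8 where the unbiased variance divides by 7, so its variance is 7/8 = 0.875 of the proper one. The factor G/(G-1) = 16/15 raises this to 7/8 × 16/15 = 14/15 = 0.933.

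- True rate = 2 × P(t14 > c × √f), with c the critical value used and f the variance factor.
- Interval width relative to the correct one = c × √f / 2.145, where 2.145 is the 97.5% point of t14.

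| Form | c | √f | c × √f | True rate | Relative width | Too narrow by |
|---|---|---|---|---|---|---|
| Uncorrected, normal | 1.960 | 0.935 | 1.833 | 8.8% | 0.855 | 15% |
| G/(G-1), normal | 1.960 | 0.966 | 1.893 | 7.9% | 0.883 | 12% |
| Uncorrected, t15 | 2.131 | 0.935 | 1.994 | 6.6% | 0.930 | 7% |
| G/(G-1), t15 | 2.131 | 0.966 | 2.059 | 5.9% | 0.960 | 4% |

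These rates need no ICC.

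**Unequal schools, by simulation of the stated model under no effect.** The main run had 16 schools split 8:8, 258 girls, 69% followed up, ICC 0.01-0.10, 50% or 80% of school variance stable, within-girl correlation 0.5, and 20,000 replicates per scenario. At size CV 0.6 it gave:

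- uncorrected, normal: 10.0-11.3%
- uncorrected, t15: 7.7-8.7%
- G/(G-1), t15: 6.7-7.9%

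A separate run (ICC 0.02-0.10, within-girl correlation 0.4, 3,000 replicates per scenario) gave 8.9-10.2% at CV 0.6 for the finite-cluster correction with a normal reference. The four forms together therefore span roughly 7-11%.

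**Small-sample methods on the same design, 8:8, CV 0 to 0.6:**

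- CR2 with Satterthwaite df (main run): 4.8-5.5%
- CR3 with t on 14 df (second run, CV 0 and 0.6): 4.0-5.3%
- t-test on school-level changes, 14 df (second run, CV 0 and 0.6): 4.5-5.5%

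**The case against.** The strongest reply is that this is a reporting gap. Nothing in the document shows that an unsuitable estimator was run, and an adequate correction may lie behind the phrase used. That stands as far as the reported results go: no inflated error rate is shown for this trial. It does not dispose of the point, because the ordinary meaning of the stated method is a sandwich without a small-sample method, and with 16 schools that form is too narrow. The software statement does not settle the matter, since no procedure or option is given. Nor do the sensitivity analyses, whose alternative specifications are not described.

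A reader might infer that the cluster level itself is open, since each girl contributes two records. Clustering on the girl would give 6.0-18.8% in the second simulation. The document does not support that reading: Methods calls the trial cluster randomized with schools allocated, and Data Analysis ties the adjustment to intra-cluster correlation. Taken together, the school is plainly the cluster, and the girl-level figures play no part in the conclusion.

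A reader might also infer that CR2 is the only adequate remedy, or that a school-level analysis must drop to the 178 girls with both surveys and so clash with intention to treat. Neither follows. CR3 and the school-level t-test also hold the level in the scenarios checked. Each school's follow-up mean can be set against its all-girl baseline mean, which keeps every baseline record. No choice of variance method resolves the 31% loss to follow-up; that is a separate matter.

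Finally, the size depends on assumed inputs. In the mildest case the excess is 5.9 - 5.0 = 0.9 points. More extreme settings, such as a 6:10 split or size CV 0.8, give larger rates but have no basis in the document and are not relied on.

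**Conclusion.** The point holds. The four intervention-effect tests rest on 16 schools, and the stated method includes no small-sample provision. On its ordinary reading the false-positive rate is 5.9-8.8% with equal schools, and roughly 7-11% at an assumed size CV of 0.6, against an assumed nominal 5%.

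All of this is conditional on 8 schools per arm; the unequal-school range also depends on the assumed correlations and school sizes. A reader might infer that the trial's p-values are wrong or its findings spurious. The document does not support that, because it does not show which form was run. This should be fixed, but it does not by itself overturn any result.

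**What to change.** In Data Analysis:

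1. State that standard errors are clustered on school, and report the variance estimator and reference degrees of freedom used.
2. Base the four p-values and intervals on a school-level small-sample method. CR2 with Satterthwaite df is one suitable choice because it keeps the stated model and all records. CR3 with t on 14 df, or a t-test on school-level changes with 14 df (each school's follow-up mean minus its all-girl baseline mean), is equally acceptable.
3. If such a method was already used, report it; only the wording changes.
4. If not, label the corrected result as specified after data collection and show the original beside it. The document is dated April 2025, and "All participant data were collected between September 2023 and July 2024".

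The cost is code and wording, with no new data. In simulation at 8:8 and CV 0-0.6, CR2 intervals were on average 4-11% wider than G/(G-1) with t15, 8-15% wider than uncorrected with t15, and 17-25% wider than uncorrected with a normal reference. P-values become somewhat larger, and a replacement made now is a post hoc choice that must be declared as one.
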